6.9. Early Termination and Relapse

Participants will be encouraged to attend study visits regardless of drinking status. Participants who miss a scheduled study appointment will be encouraged to reschedule or, if that is not possible, to attend subsequent study activities. In all cases, participants will be carefully monitored for relapse and clinical deterioration at study appointments and a detailed Safety Monitoring Plan is in place to respond to such situations. Participants who request early termination will not be followed or contacted further regarding the study.

6.10. Risks to Study Participants

6.10.1. Treatment response. It is not known if the treatment protocol proposed here will significantly modify the course of anxiety disorder or alcohol dependence for any given participant, and he/she may continue to experience the adverse consequences of these conditions during or after completion of this treatment study.

6.10.2. CBT. The main risk associated with participating in CBT is embarrassment or other discomfort participants may feel in sharing personal information with the therapist. In our experience of delivering the CBT to over 150 patients there were no reported adverse events associated with the therapy. Also, as a standard part of some of the CBT sessions participants will undergo the five-minute negative affect imagery challenge as a means of allowing them to practice newly learned coping skills in a simulated real-life situation. The content of the negative imagery challenge will be based on idiographic information provided by the patient. The challenge is designed to produce brief negative affect by imagining an actual stressful situation that occurred in the patient's recent past related to their anxiety disorder. Typically patients recover their baseline affect within several minutes after completion of the challenge. Participants are instructed and therapists are trained to avoid traumatic or highly distressing content for the imagery exercise. Ratings of discomfort are obtained throughout the exercise and therapists are trained to observe patients reactions indicating high stress responding. The patient is advised that they or the therapist are expected to discontinue the exercise if anxiety is higher than the "moderate" level target or is not tolerable to the patient. Patients may also experience discomfort when being asked to provide personal and potentially sensitive information regarding their experiences with anxiety, worry, and drinking behavior and other psychiatric / substance abuse history in the assessments. Although we do not know the likelihood of this happening, we do know that any discomfort caused by the assessments was not sufficiently great to cause any participants in our earlier study of over 300 Lodging Plus patients to discontinue the study for this stated reason or to decline to answer any of the questions they were asked.

6.10.4. Risks Due to Breach of Confidentiality and Loss of Privacy Breach of confidentiality would be potentially harmful to the psychological well-being of the patient and could have wider implications in the area of employment, insurance or interpersonal relationships. Breach of confidentiality could cause particular harm if it included sensitive or stigmatizing information

regarding medical diagnoses or history of drug use. The risk of loss of privacy in this study is judged to be minimal due to the procedures in place to protect against this.

6.11. Plan for Clinical Deterioration

6.11.1. Medical deterioration. The study physician ([name]) will be made aware of all adverse medical events related to study participants whether or not they are judged to be study related. The study physician and project coordinator will both carry a pager and will be available to all study subjects for emergencies throughout the trial. If a subject is judged by the physician to be in need of hospitalization for a medical condition, the physician will make the clinical referral immediately, and a serious adverse event report will be made to both the IRB and the sponsor. In all cases, participants will be followed for research purposes, and the data will be included in the intent-to-treat analysis and safety analyses.

6.11.2. Alcohol/drug deterioration. This clinical trial will recruit from inpatients in an alcohol dependence treatment center who will leave the treatment with the expectations of remaining abstinent from alcohol thereafter. However, based upon our past work in this population, about 40 to 60% of participants can be expected to use some alcohol over the course of the follow-up period. Participants will be seen for assessments one month, four months, and eight months following the completion of the inpatient treatment. At these assessments, the staff will closely monitor participant's alcohol consumption as part of the standard assessment battery (i.e., the TLFB interview, BAL breath test if alcohol consumption is suspected). If it is determined that a participant is currently intoxicated above .08 BAC, a car service will be called to transport participants home and hospital security will be informed that the participant's car will remain in the parking structure over night. In the case of severe alcohol deterioration, appropriate referrals to detox and/or additional alcohol dependence treatment will be made by the study physician or PI.

6.11.3. Psychiatric deterioration. We exclude individuals with severe mental illness (i.e., history of psychosis or mania) or anyone who is at imminent risk for suicide. Thus, it is unlikely that participants will experience a significant psychiatric crisis that requires additional mental health care. Suicidality is monitored at each therapy session and assessment, so any changes are monitored throughout the trial. If significant psychiatric deterioration is detected, the participant will be referred for appropriate treatment by the study physician or PI.

6.11.4. Data and Safety Monitoring Board (DSMB). An independent DSMB will monitor this project over its complete life-cycle. All three DSMB members will be faculty and senior clinical researchers/Professors in the Department of Psychiatry at the University of Minnesota who have significant experience with the protection of human subjects in clinical trials. In addition, all three DSMB members are otherwise independent of the project.

6.11.5. DSMB reports. The statistician or Project Coordinator will generate quarterly reports for the DSMB that will be reviewed by the PI prior to the DSMB meeting and will include: 1) current recruitment and attrition rates; 2) Serious Adverse Events and Adverse Events; 3) rates of data entry, data queries and data completeness; 4) the inclusion of women, children and members of ethnic minorities. Since any interim effect size might not be sufficient in size for detection, particularly on a quarterly basis given our projected recruitment, neither the PI nor the DSMB will assess efficacy and feasibility data by treatment assignment.

Dismantling the Components and Dosing of CBT for Co-Occurring Disorders

6.11.6. Serious Adverse Events (SAEs). SAEs will be defined as any significant psychiatric or medical problem requiring an overnight hospitalization at an acute care facility. Adverse Events will be defined as any adverse change in health or side effect that occurs while a participant is enrolled in the trial that is serious and unanticipated and probably, possibly, or definitely related to study participation.

6.11.7. Responsible reporter. The Principal Investigator, [name]. (licensed clinical psychologist), along with the study physician ([name].) will be responsible for accurate and timely reporting of prevalent adverse events, unexpected but study-related adverse events, and serious adverse events in the case report form, and appropriately reporting events to the local IRB and to the NIAAA Project Officer ([name]), within 48 hours for all SAEs. Other unexpected, study related or possibly-related serious events will be reported to the local IRB and to the NIAAA Project Officer within 48 hours. Additionally, all adverse events occurring during the study follow-up period will be reported to the local IRB and NIAAA Project Officer; reports will be made within 48 hours if they are SAEs. A report of the number and nature of events will be supplied to the NIAAA Project Officer ([name]) in the Annual Progress Report/Noncompeting Renewal Application.

6.11.8. Referral to treatment due to clinical deterioration. During the study follow-up phase, patients deemed by the PI, (clinical psychologist, [name].), along with the study physician ([name].), to require additional intervention due to significantly increased alcohol consumption or serious psychiatric/medical symptoms will be referred for appropriate treatment.

6.11.9. Based on the PI's reports to the DSMB, each of the three DSMB members will make a recommendation to either: 1) continue recruitment; or 2) schedule a formal DSMB meeting immediately. If the latter is recommended by any of the three members, the PC will schedule a DSMB meeting within seven days, keep meeting minutes and present a typed report to the PI with 24 hours of the meeting. At the meeting, the DSMB will vote on whether the trial should: 1) continue recruitment; 2) continue recruitment but make a protocol amendment; 3) temporarily suspend recruitment while making a protocol amendment; or 4) suspend recruitment until further investigation can be completed. If the DSMB makes any decision other than to continue recruitment, the PI will notify the IRB within 72 hours.

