6.4.1 Interviews/Diagnoses

a). Structured Clinical Interview for DSM IV (SCID). (45 minutes) Selected modules from the SCID to determine diagnostic status with reference to anxiety disorders, depression and alcohol/drug use disorders. The SCID is essentially a checklist of psychiatric diagnostic criteria (i.e., symptoms and problems) that are rated by the interviewer as "present," "absent" or "sub-clinical" or "in-determinant." This is administered at the follow-up appointments of the study.

b) Timeline Follow-Back (TLFB). (15 minutes) The TLFB interview will be used in all primary assessment to identify daily drinking patterns of patients in the four months before treatment and in the intervals between study assessments. Using a calendar, the respondent provides retrospective estimates of daily drinking over a specified amount of time.

6.4.2 Questionnaire Packets (1 to 1.5 hours) (Each questionnaire takes about 5 minutes to complete and typically includes 20 multiple choice questions or less) (References and rationale for questionnaires are provided below).

a) Anxiety.

- State-Trait Anxiety Inventory (STAI)
- Penn State Worry Questionnaire (PSWQ)
- Beck Depression Inventory (BDI)
- Panic Disorder Severity Scale (PDSS)
- Social Phobia Scale (SPS)
- Inventory of Depression and Anxiety Symptoms (IDAS)
- Perceived Stress Scale (PSS)

b) Alcohol.

- Alcohol Expectancy Questionnaire (AEQ)
- Inventory of Drinking Situation (IDS)
- Situational Confidence Questionnaire (SCQ)
- Obsessive-Compulsive Drinking Scale (OCDS)
- Addiction Severity Index (ASI)
- Reasons for Drinking Questionnaire (RFDQ).
 - Drinking to Cope Questionnaire (DCQ)
 - Negative Emotions and Use Questionnaire (NEUQ)

c) Other

- Demographics
- Treatment Services Summary (TSS)
- Suicidality Questionnaire (SQ)
- Personality Inventory for DSM-5 Brief Form (PID-5)

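### The AE and SAE definitions leave out non-serious harms, and serious events without overnight admission that are judged unrelated or anticipated, so these are not assured of formal recording or DSMB reporting

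*Combined protocol and SAP*

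**What the plan says.** Section 6.11.6 sets the SAE criterion: "SAEs will be defined as any significant psychiatric or medical problem requiring an overnight hospitalization at an acute care facility". It then limits an AE to a health change or side effect during enrolment "that is serious and unanticipated and probably, possibly, or definitely related to study participation". Section 8.3.3 repeats both definitions, so this is not a slip in one place.

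The DSMB report described in 6.11.5, and again in 8.3.2, has one item on harms: "2) Serious Adverse Events and Adverse Events".

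Other safety text is wider:

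- Section 6.11.1: the study physician "will be made aware of all adverse medical events related to study participants whether or not they are judged to be study related".
- Section 6.11.3: "Suicidality is monitored at each therapy session and assessment, so any changes are monitored throughout the trial". A suicidality questionnaire is also listed in 6.4.2.
- Section 6.11.7: responsibility extends to "reporting of prevalent adverse events, unexpected but study-related adverse events, and serious adverse events in the case report form". Section 8.3.4 uses the same categories and adds a duty to report events to the DSMB. Neither section explains what a *prevalent* event is.
- Section 6.11.7 also puts other serious events that are unexpected and related or possibly related on a 48-hour clock to the IRB and NIAAA, with no hospitalisation condition. It adds that "all adverse events occurring during the study follow-up period will be reported to the local IRB and NIAAA Project Officer".

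**The concern.** The AE definition joins three conditions with *and*. Seriousness, expectedness and relatedness are normally attributes recorded about an event once it has been captured. Here they decide whether it is an AE at all. A harm that is non-serious, or foreseen, or judged unrelated therefore fails the definition.

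The SAE definition has the opposite gap. It asks nothing about cause or expectedness, but it rests on a single outcome. Death, danger to life and attempted suicide are not named, so they count only when they involve an overnight acute-care stay.

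This matters in this population. Section 6.10.2 names distress during the imagery exercise and discomfort during assessments as known risks; because they are foreseen, they do not qualify as AEs. Section 6.11.2 expects about 40 to 60% of participants to drink during follow-up, so drinking-related harm short of admission could readily be judged anticipated. Section 6.11.3 answers detected psychiatric deterioration with referral and specifies no event report. A low AE count at the end of the trial could then reflect the definition as much as the safety of the three therapies.

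**Working it through.** No arithmetic applies: the point depends on no alpha, power, effect size or sample size. The check is to run event types through the definitions in 6.11.6 and 8.3.3, then look for any other route in 6.11.1, 6.11.3, 6.11.7 and 8.3.4.

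| Event | AE? | SAE? | Other route |
|---|---|---|---|
| (a) Non-serious harm, any cause | No | No | Physician told if medical; may be recorded if it counts as *prevalent* |
| (b) Death, life-threatening event or suicide attempt, no overnight admission, unanticipated and at least possibly related | Yes, if *serious* has its ordinary meaning | No | 48-hour report to IRB and NIAAA (6.11.7) |
| (c) Same events, judged unrelated or anticipated | No | No | Physician told if medical; suicidality monitoring of participants still attending |
| (d) Significant problem with overnight acute-care admission, any cause | Only if also unanticipated and possibly related | Yes | 48-hour SAE report (6.11.7) |

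**What follows**

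1. Rows (a) and (c) meet neither definition. The DSMB report names only AEs and SAEs, so it need not contain them.
2. Row (b) is captured, but this depends on a word the documents do not define outside the SAE criterion. If *serious* were taken to mean SAE-level, and so hospitalised, row (b) would also fall out.
3. Rows (b) and (d) show that the definitions overlap and that neither contains the other. An event in (b) is an AE and not an SAE. An admission judged unrelated is an SAE and not an AE.

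**Against the wider text**

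- Section 6.11.1 governs what the physician is told. It is not a recording rule or a DSMB reporting rule, and it speaks of medical events.
- The follow-up reporting rule in 6.11.7 covers all AEs, but it uses the defined term and so inherits its limits.
- The *prevalent* category suggests wider recording on the case report form. Without a definition, staff cannot tell whether an event in row (a) or (c) belongs there.
- The timing for other serious events differs: 48 hours in 6.11.7, but promptly and in line with reporting requirements in 8.3.4. In both places that rule names the IRB and NIAAA, not the DSMB.
- Section 6.11.1 says data will enter safety analyses. Section 7 describes none.

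**The case against.** The strongest reply is that harms are watched through several channels besides the AE and SAE labels, and that the therapy is low risk. Section 6.10.2 reports no adverse events from the CBT in over 150 patients. Much of this reply stands, and it rules out several stronger readings a reader might draw.

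- *Deaths and suicide attempts without admission escape safety capture altogether.* Not supported. Those that are unanticipated and possibly related fit the AE definition on its ordinary reading and fall under the 48-hour rule in 6.11.7. The physician hears of adverse medical events regardless of cause, and suicidality is checked at each session and assessment.
- *The number of non-serious AEs must be zero in every arm.* This does not follow. Sections 6.11.7 and 8.3.4 call for *prevalent* events on the case report form, and where sections conflict the narrowest cannot be taken to fix the count.
- *The arms could not be compared on worsening anxiety.* Not supported. Anxiety questionnaires are given in all arms at baseline, post-treatment and follow-up (5.2, 6.4.2), and 7.8 compares baseline to post-treatment change by group.
- *The DSMB has no other source.* Section 8.3.4 gives the principal investigator a separate duty to report events to it, and its report also covers attrition, data completeness and inclusion.
- *The AE definition is simply narrower than the SAE definition.* It is not; they overlap. For the same reason, the assumption in 6.11.7 that some AEs are not SAEs is not in itself a contradiction.

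It is also fair to say that a wide duty to inform the physician can coexist with a narrower reporting definition. What the reply does not supply is a rule that assures recording and DSMB reporting for rows (a) and (c). The earlier experience with the CBT does not settle this, since the documents do not say which definition lay behind that count.

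**Conclusion.** The point holds as a defect in the event definitions. As written, non-serious harms, and deaths, life-threatening events or suicide attempts without overnight admission that are judged unrelated or anticipated, are neither AEs nor SAEs. They are not assured of formal recording or of inclusion in the DSMB report. Capture is incomplete, not absent.

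The size cannot be given in events: the documents contain no rates for such harms. No efficacy estimate, test or sample size changes. What is affected is the completeness of the harms data and the meaning of any AE count reported from them.

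Two assumptions matter. First, *serious* in the AE definition and in the 48-hour rule is read in its ordinary sense; tying it to hospitalisation would widen the gap. Second, that 48-hour rule is read as requiring an event to be unexpected and also related or possibly related. If these were alternatives, fewer events in row (c) would go unreported to the IRB and NIAAA, but the DSMB report would be unchanged. That both readings are open is itself a reason to reconcile the sections.

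**What to change.** Reconcile 6.11.1, 6.11.6, 6.11.7, 8.3.3 and 8.3.4 around one pair of definitions:

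- **AE:** any untoward change in health after consent, with seriousness, expectedness and relatedness recorded as attributes rather than used as entry conditions.
- **SAE:** an AE that results in death, is life-threatening, leads to hospitalisation or lasting disability, or is otherwise medically important, including a suicide attempt.

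Define or delete the *prevalent* category, give one reporting time for other serious events, and state in 6.11.5 and 8.3.2 that the DSMB report uses the new definitions. Section 7 should describe the safety analyses that 6.11.1 promises.

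If data collection has ended, state the definitions that were in force when reporting harms, and reclassify recorded events under the wider ones as far as the records allow.

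The cost is protocol wording and some additional event forms.

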6.12. Time

Total amount of time, including completion of self-report forms, should not exceed 50 hours (excluding travel time).

6.13. Location

All study activities will take place at the University of Minnesota Hospital located at [name]. All study activities take place in the same building on the second floor in the University of Minnesota's Ambulatory Research Center (ARC). The ARC provides devoted space for clinical research with a full time receptionist, a waiting room and private interview/therapy rooms.

6.14. Treatment and Compensation for Injury

In the event that research activity results in an injury, treatment will be available, including first aid, emergency treatment and follow-up care as needed. Care for such injuries will be billed in the ordinary manner to the patient or his/her insurance company.

6.15. Costs and Reimbursement of Subjects

The only costs to participants is travel to Fairview for the three follow-up assessments at 1-, 4-, and 8-month follow-ups. Participants will be reimbursed for their time for all study activities. A total of \$330 can be earned for each participant that completes each study task. (The exact payment per task is shown in Table 2 above). Payments are made within one business day of the completion of each study task via a Greenphire Clincard. Reimbursements for the follow-up visits are graduated (increased for later follow-ups) reflecting the greater value of these data to the aims of the study and our experience indicating that participants' motivation to attend follow-up assessments decreases with increasing time since the initial treatment. Note participants recruited after approval of MOD00013885 will not complete the eight-month follow-up visit and will therefore be compensated up to \$230.

6.16. Confidentiality of Records

Research records are coded by number and the master list matching subject numbers to names is kept by the study statistician and Research Coordinator. All data are stored in a locked cabinet and password protected computer files. The only exception to this is data obtained with the subjects' permission.

7.0 STATISTICAL CONSIDERATIONS

7.1. Data management

The database will be created and maintained by BDAC staff and will be stored on a security-enabled server (HIPAA-compliant, firewall protected) to be accessed only by designated study personnel. The database for the study will use REDCap (consortium agreement through the University of Minnesota's CTSA) via a web-based interactively edited data entry with secure login through the

University of Minnesota. Data quality control will be monitored regularly within the REDCap data system by [name].

7.2. Data quality/integrity

All data will be inspected for missing and outlier values and response set patterns. Distributions will be graphically represented and inspected visually and quantitatively for departures from normality and other irregularities. All data will be characterized in terms of means, standard deviations, histograms, and response ranges for continuous variables and frequencies and counts for categorical variables. A random sample of 5% of cases will have all hard copy data compared to entered data for accuracy, including all measures scored by computer algorithms. The need for data re-entry or recoding, data transformations and non-linear or non-parametric analyses will be based on these results.

